4.1 Exclusion Criteria

Individuals will be excluded if:

- Individual does not reside as a long-stay resident in one of the nine participating UCH NH locations partnering with the PI for this project.
- Resident does not have both a BIMS score of 0-12 *and* a non-zero response on PHQ-9 items of anhedonia, sad mood, poor self-esteem, poor appetite, or restlessness or Section E behavior item(s).

4.2 Study Enrollment Procedures

Seven UCH NH communities in Ohio will be invited to participate in the IPPI program. [name] will visit in person to talk with the leadership team of each community and secure participation. The 7 sites have an average of 100 beds with approximately 50% of residents living with dementia.

Leadership Staff: The UCH staff implementation team at each site may include the Director of Nursing, Life Enrichment Director, and direct care providers (State Tested Nursing Assistants; STNAs) also known as Care Partners. These individuals will be asked to complete an exit interview for which we will seek informed verbal consent.

We will seek staff volunteers to be a part of the UCH implementation team. [name] will meet with staff in each community, explain the IPPI project, the time commitment, and work with leadership to develop an implementation team that includes one or two champions(s) and 2-3 care partners.

Residents: UCH implementation team champion(s) will be trained to use MDS data to identify residents who are optimal for the IPPI program. Eligible residents will be indicated by a Brief Inventory for Mental Status (BIMS) score of 0-12 (a screening to identify individuals with cognitive impairment) and who have recently communicated distress as reported in Section D (non-zero response on PHQ-9 items of anhedonia, sad mood, poor self-esteem, poor appetite, or restlessness) or Section E (non-zero response on a behavior) within each community.

Implementation Team: The UCH implementation team will be invited to be trained to deliver the IPPI program. They will have choice in the activity that they will do with the resident, and will be offered coaching and feedback. Trained care partners will be asked to conduct 2 IPPI activities per week with each identified resident. Selected residents will be engaged with the IPPI program on a rolling basis immediately after their quarterly MDS assessment (pre-test) over 6 months. The provider UCH utilizes a consistent staffing approach, and the idea is that the IPPI activities are integrated into routine care practices with selected residents.

5 STUDY INTERVENTIONS

5.1 Interventions, Administration, and Duration

IPPIs will be conducted by trained care partners for each identified eligible resident. Enrollment will occur on a rolling basis, upon completion of an initial MDS 3.0 assessment (i.e., annual or quarterly assessment, whichever is completed at that time). Upon determination of eligibility, site champion(s) will 1) assess resident important preferences with the 16 preferences required to be collected in Section F of the MDS (e.g., being around animals such as pets, choose what clothes to wear, going outside), 2) match a resident's important preferences with 1-2 appropriate IPPI protocols, 3) invite one or more of the implementation team care partners to select one of the IPPI protocols to conduct with the resident, 4) coach the care partner(s) on how to lead the activity, 5) have the care partner(s) lead the one-to-one activity with the champion watching to give feedback, 6) have care partners conduct IPPIs with a resident for approximately 10 minutes 2 days per week, at a time convenient for both the care partner and resident.

IPPIs will continue to be offered for 6-months from date of study initiation. IPPIs will be conducted within the NH in the resident's room or a common area, or outside the NH as appropriate for meeting the preference targeted. Care partners will select from 60+ pre-created IPPI protocols and complete the interventions accordingly.

The IPPI involves minimal risk since the resident can decline and is based on his or her preference. Further, IPPI will not adversely impact the rights and welfare of residents because it will involve a meaningful and enjoyable use of time with a care partner.

Handling of Study Interventions

All participating NH communities will be provided a body of IPPI activity manuals; each IPPI activity has a corresponding toolkit with instructions and supportive conversation prompts that consist of an introduction, middle, and conclusion section. The IPPI program has been explicitly designed for PLWD who are experiencing symptoms of distress. We will assess both fidelity and adherence to the IPPI protocols during implementation.

5.2 Concomitant Interventions

5.3.1 Allowed Interventions

IPPI intervention activities will be allowed for all eligible residents.

5.3.2 Required Interventions

IPPI intervention activities will be offered to all eligible residents, but residents have the right to refuse participation prior to starting each IPPI or anytime during an IPPI activity.

5.3.3 Prohibited Interventions

No prohibited interventions are noted. All other usual care interventions for residents can continue as needed during the course of the IPPI pilot implementation process.

5.3 Adherence Assessment

Adherence to the study regimen is defined as completion of at least 80% of designated IPPI sessions per eligible/enrolled resident. Adherence to completion of two 10-minute IPPIs per week over the course of 6-months (e.g., 48 sessions total) will be tracked in the UCH EMR upon completion of each IPPI activity with each resident (see evaluations section below).

6 STUDY PROCEDURES

The Schedule of Evaluations in section 6.1 includes all study evaluations.

6.1 Schedule of Evaluations

Assessment	Pre-enrollment	Baseline, Enrollment (Day 0)	Each IPPI (2x a week for 180 days)	3-month Assessment (~Day 90)	6-month Assessment (~Day 180)	Post Intervention Trial
Organizational Readiness for Implementing Change (ORIC)	X					
MDS 3.0 data of residents BIMS scores and Section D and E Responses (rolling ; each resident assessed for enrollment to serve as baseline assessment, 3-mon, and 6-mon)	X	X		X	X	
Identify Implementation team (Y/N)	X					
Virtual Coaching session attendance (Y/N)	X			X	X	
Emotion-Focused Communication Training (EFCT) completion (Y/N)	X					
Emotion-Focused Communication Training (EFCT) pre and post-test (knowledge, efficacy)	X					
IPPI Training (watching 2 videos) completed (Y/N)	X					
Resident Preferences Worksheet (rolling)		X	X	X	X	
Care Plan Documentation (Y/N)		X	X	X	X	

Fidelity Assessment with Pragmatic Checklist (observation of 1st IPPI between each resident and implementation team member delivering IPPI)			X (1 st IPPI only)			
Exit Interview (communication, acceptability, feasibility, appropriateness, facilitators, and barriers)						X
Troubleshooting (count of contacts)	X	X	X	X	X	
Intervention Withdrawal form			X			
Adverse Events form			X			

6.2 Description of Evaluations

6.2.1 Pre-enrollment

These evaluations occur prior to enrollment of NH residents to the intervention.

Organizational Readiness

To understand each NH's organizational readiness for the intervention, each implementation team member will be asked to complete the ORIC assessment.

Identifying subjects (Screening)

UCH site champions will be trained to identify eligible residents in each community using MDS 3.0 BIMS data (score of 0 to 12) and documentation of distress as indicated by a non-zero response in Section D on PHQ-9 items of anhedonia, sad mood, poor self-esteem, poor appetite, or restlessness or a non-zero response on a Section E behavior.

Identification of eligible residents will occur on a rolling basis, following completion of a given resident's quarterly or annual MDS 3.0. Upon review of MDS 3.0 assessments at the care planning meeting, if a resident triggers for cognitive impairment and distress, the person will be identified as eligible for the IPPI program. As a rolling process, site champion(s) and care partners will identify any newly eligible residents who have completed their quarterly or annual MDS 3.0 assessments and trigger for cognitive impairment and distress. This process will likely result in adding 3-8 residents per month for 3-4 consecutive months.

Baseline MDS 3.0 assessments (includes BIMS and Distress data) and two subsequent MDS 3.0 assessments (at approximately 3 and 6 months), along with EMR data that document the IPPIs will be provided to PI approximately half-way and at the completion of the project by the UCH corporate IT officer via a secure file transfer service. The half-way point will be when all enrolled residents are past their 3-month post IPPI initiation. The completion of the project will occur 6 months post IPPI initiation. Data for all residents will be provided and the PI will link the MDS and EMR data, extract residents engaged in the IPPI project, deidentify, and add a unique ID number for each participant prior to providing data to the Statistical Consultant, [name] via a secure file transfer service.

Implementation team training

To track implementation efforts, each NH site champion(s) will be asked to record on paper forms located in a binder (see Appendix A) that assess the following yes/no questions prior to starting to implement the IPPI with residents: Did the site identify an implementation team (Y/N); Did the implementation team attend the virtual coaching session (Y/N); did the members of the implementation team complete the EFCT (Y/N); and did the implementation team complete the IPPI training (Y/N).

In addition, all implementation team members (i.e., site champion, care partners) at each NH will be asked to complete the EFCT. As a part of the online EFCT course, they will be asked to complete a pre- and post-assessment on knowledge and self-efficacy. The post-assessment will also contain questions assessing acceptability. To

assess knowledge gained from the content of the intervention, participants will respond to 16 intervention specific multiple-choice or multiple-response items prior to training (pre-assessment) and upon completion of the training (post-assessment). Items were created to specifically check learning on all key course elements. Items assess knowledge regarding ways to recognize and respond to emotions (e.g., anger, pleasure). A total count of correct answers is computed (possible range: 0 to 27; note, total exceeds 16 as some questions required more than one correct response to be selected). For self-efficacy, consistent with Bandura's (1997) initial conception of self-efficacy that it is behavior-specific, we created items modeled after Fortinsky and colleagues' (2002) and Steffen and colleagues' (2002) work with caregivers, that were tailored to the specific intervention content presented in the EFCT. By using a tailored set of items created specifically for this course, the impact of the specific intervention activities can be assessed. The scale includes 9-items asking participants how confident on a scale of 0 (*not at all confident*) to 10 (*certain you can do it*) they are completing the proposed activity. Items assess confidence in identifying one's own feelings, ability to respond effectively to those emotions, identifying emotions in others, and responding effectively to their emotions. A mean-item total score is computed (possible range: 0 to 90; $\alpha = .90$). Third, post-training program acceptability will be assessed with three metrics. Drawing upon the Implementation Research Measure for program acceptability, appropriateness and feasibility of Proctor et al. (2011) and Weiner et al. (2017), we assess Acceptability of the Intervention Measure (AIM) and Intervention Appropriateness (IAM) with two 4-item scales. Items are rated from 1 (*completely disagree*) to 5 (*completely agree*). AIM includes items such as "*The Emotion-Focused Communication Training is appealing to me*" ($\alpha = .92$; range 4 to 20). IAM includes items such as "*The Emotion-Focused Communication Training seems applicable*" ($\alpha = .94$; range 4 to 20). In addition, we assess general ratings of program satisfaction with 5-items, such as "*Overall, I was satisfied with this training*" ($\alpha = .92$; range 5 to 25).

6.2.2 Enrollment, Baseline, and/or Randomization

Enrollment

There will be a waiver of consent for all residents enrolled in the program. Upon identification of eligibility, the implementation team uses the Resident Preferences Worksheet to identify next steps. This will be a rolling process as individuals are identified as eligible to participate. Each enrolled individual will have a Worksheet completed at their specific time of enrollment. In this Worksheet, members of the implementation team will identify the resident's important preferences and identify matching IPPI protocols that can be used. They will also identify the behavior they hope to target with the IPPI intervention. A copy of the care plan will be obtained to ensure that the targeted behavior is addressed. The PI will collect this Worksheet from champions to determine whether or not the IPPI protocols were appropriately matched to important resident preferences as a measure of implementation fidelity every three months.

Baseline Assessments

The baseline assessment for residents will be their most recent MDS 3.0 (either

annual or quarterly). The BIMS and Section D/Section E responses will be provided to the PI for each enrolled resident by the UCH IT professionals. These data will include the targeted mood or behavior selected by care partners at enrollment. The type of mood or behavior item being targeted will be different for each resident (e.g., wandering for one, verbal behavior for another).

6.2.3 Follow-up Visits

- IPPI completions 2x weekly:
 - The Fidelity Assessment with Pragmatic Checklist will be completed the first time a member of the intervention team completes an IPPI with a resident. This will be completed by the site champion when shadowing the care partner in implementation.
 - IPPIs will be documented in the UCH EMR through Point-Click-Care.
 - During implementation, troubleshooting (count of contacts of the implementation teams with the PI/Project team) will be recorded.
 - If an eligible resident is withdrawn from participation, the withdrawal date, and the reason will be documented on an Intervention Withdrawal form and provided to the project PI. This form is part of the binder that will be provided to each site champion(s).
 - Adverse Events will be reported directly to the PI if they occur as per section 7.3 below.
- 3-months (~90 days):
 - Distress data (Section E and Section D) from the next completed MDS 3.0 assessment (annual or quarterly) will be provided to the PI by the UCH IT Corporate office. The Centers for Medicare and Medicaid Services require completion of an assessment every 3-months; however, experience indicates that there is individual variability in actual completion times and therefore we will not enforce a strict allowable time window for these data. Change in each Section E/Section D item will be scored as 0 = *stayed the same as baseline* (e.g., score on MDS 3.0 baseline assessment equals score on MDS 3.0 follow-up assessment), 1 = *got better* (e.g., score on MDS 3.0 baseline assessment is better (lower) than the score on the MDS 3.0 follow-up assessment), or 2 = *got worse* (e.g., score on MDS 3.0 baseline assessment is worse (higher) than the score on MDS 3.0 follow-up assessment) for our primary, person-centered clinical outcome.
- 6-months (~180 days):
 - Distress data (Section E and Section D) from the next completed MDS 3.0 assessment (annual or quarterly ~6-months post baseline assessment) will be provided to the PI by the UCH IT Corporate office. The Centers for Medicare and Medicaid Services require completion of an assessment every 3-months; however, experience indicates that there is individual variability in actual completion times and therefore will not enforce a

strict allowable time window for these data. Change in Section E/Section D items will be scored as 0 = *stayed the same as baseline* (e.g., score on MDS 3.0 baseline assessment equals score on MDS 3.0 follow-up assessment), 1 = *got better* (e.g., score on MDS 3.0 baseline assessment is better (lower) than the score on the MDS 3.0 follow-up assessment), or 2 = *got worse* (e.g., score on MDS 3.0 baseline assessment is worse (higher) than the score on MDS 3.0 follow-up assessment) for our primary, person-centered clinical outcome.

6.2.4 Completion/Final Evaluation

Each enrolled resident will receive 6-months of the IPPI intervention. Upon completion of the intervention an Exit Interview will be completed with implementation team members at each NH site. Members of the implementation team will be invited to participate in a semi-structured interview with researchers at the end of the project. The Exit interview (see Appendix B) will contain open-ended questions about communication and facilitators and barriers. It will also include close-ended questions on acceptability, feasibility, and appropriateness using the Implementation Research Measure for program acceptability, appropriateness, and feasibility of Proctor et al. (2011) and Weiner et al. (2017).

7 **SAFETY ASSESSMENTS**

Once an individual is enrolled in the study, participant safety will be monitored. Enrollment is defined as a resident identified as eligible based on most recent MDS 3.0 assessments and then having a completed Resident Preferences Worksheet.

No known risks of the intervention are anticipated. The potential risks or discomfort are minimal to the organization, residents, and care partners. This intervention is focused on a positive interaction around the preference of the resident and their care partners, such as a sing-a-long activity, or going outside when the weather is good. The activities can be stopped if the resident or care partners experience distress, however that is unlikely to occur as the intervention found that residents had increased positive affect during and after the intervention. Residents can refuse to participate any time a care partner seeks to engage with them.

However, a person could become agitated during an IPPI if it is not explained well by a care partner, as with routine care. In these instances, behaviors such as wandering or becoming aggressive could occur at the same rate with which they occur during typical clinical care. Further, the population served by this intervention is by definition a vulnerable medical population experiencing dementia and often multiple other chronic illnesses. We would expect that due to the age and illness severity of the PLWD that the occurrence of falls, emergency room/hospitalizations, and death can reasonably be expected. Implementation team care partners are already trained by their specific facility in managing safety concerns and health events that may occur during typical care and they will behave the same during enrollment in the IPPI program. The care partners would act according to their facility's rules and expectations.

In the case of an adverse event occurring during study participation, an Adverse Event

form would be submitted to the PI within 3-days of the event (see procedural expectations below in 7.3). In the case of death of a resident, the site champion will be advised to call the PI to notify her of the passing.

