7.3.1 Reporting Procedures

In the occurrence of an AE or SAE, during an IPPI, the implementation team will be instructed to complete the column in the provided binder on the final column of the resident preferences worksheet, providing a description of the event, the timing of the event, and the anticipated clinical response. If warranted, the team will be instructed to complete the IMPACT Serious Adverse Event (SAE) Report Form.

If an AE or SAE becomes apparent during a monthly call, the PI will request a completion of an Adverse Events or IMPACT Serious Adverse Event (SAE) Report Form, as applicable.

In the case of death, the site champion will also be instructed to call the PI to relay this information.

Following typical clinical safety protocols of the specific NH, a determination of continuation in the IPPI program will be determined by the NH clinical implementation team based on severity of event and relationship to the study. The decision for care alteration or necessary withdrawal from the study will be communicated with the PI through the Adverse Events form and/or if necessary, the second to last column of the Resident Preferences Worksheet. That column asks if the resident completed the IPPI program and if no, why not. For reporting, the decision of relatedness, expectedness, and severity of events will be defined as follows:

Severity of Event

All AEs will be assessed by a qualified medical professional on the NH implementation team using a protocol defined grading system to describe severity.

- Mild – Awareness of signs or symptoms, but easily tolerated and are of minor irritant type causing no loss of time from normal activities. Symptoms do not require therapy or a medical evaluation; signs and symptoms are transient.
- Moderate – Events introduce a low level of inconvenience or concern to the participant and may interfere with daily activities but are usually improved by simple therapeutic measures; moderate experiences may cause some interference with functioning.
- Severe – Events interrupt a participant’s usual daily activity and may require systemic treatment. Severe events are usually potentially life-threatening or incapacitating. Of note, the term “severe” does not necessarily equate to “serious”.

Expectedness

- Unexpected - Nature or severity of the event is not consistent with information about the condition under study or intervention in the protocol, consent form, product brochure, or investigator brochure.

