All adverse events that are serious (SAE) and unexpected (i.e., have not been previously reported for the study’s intervention) will be reported to the IMPACT Collaboratory Regulatory and Data Team Leader ([name]), NIA IMPACT Collaboratory PO ([name]), and the IMPACT Collaboratory Safety Officer within 48 hours of the study’s knowledge of SAE.

- Only those adverse events that are serious (SAE), unexpected, and related to the intervention must also be reported to Advarra IRB. Unexpected and unrelated SAEs will be reported to Advarra IRB on a case-by-case basis if requested by the IMPACT Collaboratory Safety Officer or NIA IMPACT Collaboratory PO.

All deaths will be reported to IMPACT Collaboratory Regulatory and Data Team Leader ([name]), NIA IMPACT Collaboratory PO ([name]), and the IMPACT Collaboratory Safety Officer within 24 hours of study’s knowledge of death.

- Advarra IRB does not require the specific reporting of death outside of the SAE reporting requirement above, but they will be notified on a case-by-case basis if requested by the IMPACT Collaboratory Safety Officer or NIA IMPACT Collaboratory PO.

All unanticipated problems (UPs) will be reported to the IMPACT Collaboratory Regulatory and Data Team Leader ([name]), Advarra IRB, NIA IMPACT Collaboratory PO ([name]), and the IMPACT Collaboratory Safety Officer within 48 hours of the study’s knowledge of the event.

The summaries of all previously reported unexpected and related SAEs, deaths, and UPs, as well as all other SAEs and AEs will be reported to IMPACT Collaboratory Regulatory and Data Team Lead ([name]), Advarra IRB, NIA IMPACT Collaboratory PO ([name]), and the IMPACT Collaboratory DSMB Chair (or the project’s Safety Officer) at a minimum every 6 months, or at a frequency requested by the IMPACT Collaboratory Safety Officer or NIA IMPACT Collaboratory PO.

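### Sites have 3 days to report any adverse event to the PI and no set time for the call about a death, while onward limits of 48 and 24 hours run from a moment of study knowledge that is never defined

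*Combined protocol and SAP*

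**What the plan says.** Site to PI. The opening text of Section 7 states that, for an adverse event during participation, an Adverse Event "form would be submitted to the PI within 3-days of the event", and refers to 7.3 for procedures. Sections 7.3 and 7.3.1 contain no other site-to-PI time limit and no separate one for serious adverse events (SAEs). Section 6.2.3 also refers only to 7.3.

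Deaths. Section 7 says "the site champion will be advised to call the PI to notify her of the passing". Section 7.3.1 repeats it: "In the case of death, the site champion will also be instructed to call the PI to relay this information". Neither sentence gives a time.

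PI onward. Under Section 7.3.1, "All adverse events that are serious (SAE) and unexpected" go to the collaboratory's regulatory lead, the NIA programme officer and the Safety Officer "within 48 hours of the study’s knowledge of SAE". Unanticipated problems have the same 48 hours. Deaths go to the same recipients, "and the IMPACT Collaboratory Safety Officer within 24 hours of" the study's knowledge. The text available does not define that knowledge.

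Other routes. Section 7.3.1 has the team enter an event that occurs during a session in the last column of the Resident Preferences Worksheet, and complete the SAE form if warranted. Section 6.2.2 has the PI collect worksheets every three months. Section 16 asks champions to send binder forms in batches with the 3- and 6-month data, with no exception for event reports. The monthly call is a further check: "If an AE or SAE becomes apparent during a monthly call, the PI will request a completion" of the relevant form.

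**The concern.** The onward limits separate serious from non-serious events and are stated in hours. The rule given to the people who see the events makes no such separation and is stated in days. The two are joined only by a phrase whose meaning is left open, so the protocol does not settle whether a site that uses its full allowance is compliant.

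What is at stake is how soon the Safety Officer hears of an unexpected serious event or a death while the intervention continues at up to seven homes. Section 10.3.1 says that implementation team staff receive no training in human-subjects research, so they cannot be expected to infer a faster rule than the one written for them. Sections 7 and 7.3 anticipate falls, hospitalizations and deaths in this population, so the death route is likely to be used.

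**Working it through.** The plan gives no figure of its own to reproduce. The check is arithmetic on the stated limits.

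Inputs:
- Site to PI, any adverse event: 3 days = 3 × 24 = 72 h, counted from the event (Section 7).
- Site to PI, call about a death: no time stated (Sections 7 and 7.3.1).
- Onward, serious and unexpected events, and unanticipated problems: 48 h from study knowledge (7.3.1).
- Onward, deaths: 24 h from study knowledge (7.3.1).
- A death meets the SAE definition in 7.3 and is therefore an adverse event, so the 3-day form can be read to cover it.

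Reading A: knowledge begins with site staff. Assume that they know at the time of the event. Time left when a form sent at the limit reaches the PI = onward limit − site limit.
- Unexpected SAE or unanticipated problem: 48 − 72 = −24 h.
- Death, by the form: 24 − 72 = −48 h.

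Both limits have passed before the PI hears. If the home itself learns d hours after the event, the overruns shrink to 24 − d and 48 − d hours. They vanish only when the home learns at least 24 h or 48 h late, respectively.

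Reading B: knowledge begins with the PI. The limits run one after the other. Latest compliant report after the event = site limit + onward limit.
- Unexpected SAE or unanticipated problem: 72 + 48 = 120 h (5 days).
- Death, by the form: 72 + 24 = 96 h (4 days).
- Death, if only the undated call applies: no upper bound.

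Under this reading the full 48 h or 24 h is still available and nothing is breached.

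Batch route. Section 7.3.1 uses the worksheet as a place of record for events during a session, Section 6.2.2 has it collected every three months, and Section 16 batches the binder forms at 3 and 6 months. Read literally, that conflicts with the 3-day rule, and no sentence says which prevails.

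Can compliance be checked? The SAE form in Appendix A records onset as a two-month window and has no field for when the home or the PI became aware. Neither the 24 h nor the 48 h limit can be verified from it.

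**The case against.** The strongest reply is that the onward clocks run from knowledge, not from the event, and that the PI reading fits the text better. Forms are submitted to the PI, and the champion calls to notify her. Section 7.3.2 makes champions recorders of reportable events, not onward reporters. On that reading the rules are compatible. This stands, and it rules out a conclusion that a reader might draw: that the 24- and 48-hour limits cannot be met. That follows only if site knowledge counts. The site reading nonetheless remains open, because champions record all reportable events and clinical staff at the home grade severity and help judge relatedness.

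Three other strong inferences are not supported:
- That deaths have no deadline at all. Only the call is undated; the 3-day form can be read to cover a death, and the call comes in addition to it.
- That the monthly call permits a delay of about a month. An SAE that first surfaces weeks later has already missed the 3-day rule. The call is a back-up.
- That the delay can be counted in further sessions for the affected resident. This cannot apply to a death, and the documents leave decisions on continuing to the home's clinical staff (7.3.1, 8), with facility safety procedures in force throughout.

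It is also fair that the 48 h channel covers only serious and unexpected events plus unanticipated problems, so many hospitalizations or falls may lie outside it. The protocol does not state the purpose of the limits, and it describes the risk as minimal. These points restrain the severity. They do not supply the missing definition or a prompt site step.

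**Conclusion.** The concern holds in a conditional form. The documents leave the start of the onward clock undefined, give sites no faster step for serious events, and put no time on the call about a death. If site knowledge counts, a site using its permitted 72 h overruns the limits by 24 h for an unexpected SAE or unanticipated problem and by 48 h for a death. If only PI knowledge counts, reports can arrive up to 120 h and 96 h after the event with no rule broken, and a death carried only by the undated call has no bound.

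These figures assume that the site uses its whole allowance, that the home knows at the time of the event, and, for the 48 h overrun and the 96 h figure, that the form rule covers deaths. Part of the roster and site pages was not available, so whether champions are listed there as study staff could not be checked.

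This should be corrected, because following the 3-day rule exactly can delay expedited reports under either reading. It is not evidence that the limits are impossible to meet or that any resident would be harmed.

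**What to change.** Reconcile Sections 7, 7.3.1 and 16:
- Keep 3 days for non-serious adverse events.
- Add a separate site-to-PI notification for SAEs, unanticipated problems and deaths, short enough to fit inside the onward limits. One example is a phone call within 24 h of the home's awareness, with the form to follow. If home awareness starts the clock, that leaves 48 − 24 = 24 h for an unexpected SAE but 24 − 24 = 0 h for a death, so the call about a death must come sooner.
- State whose awareness starts the study's knowledge.
- Exempt event reports from batch submission and from the three-monthly worksheet collection.
- Record the date and time at which the home and the PI each became aware, so that compliance can be checked.

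The cost is an edit to the protocol, the binder instructions and one form, and a few more prompt calls by champions. A call about a death is already planned and needs only a time. The help line in Section 7.1 exists for adapting activities, so its purpose would have to be widened if it is used for event reports.
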